16.4 Sample Size Determination

The proposed trial design is a randomized phase II trial with a 1:1 randomization ratio with the stratification variable noted in section 5.1. The primary endpoint for this trial is the 24-month complication rate, as defined above. The study will plan to enroll a total of 72 evaluable patients. An evaluable patient is defined as a patient who receives any dose of the protocol-defined radiotherapy. In this trial, we will accrue and randomize up to 96 patients over 3 years to account for ineligibility, cancellations (withdrawals prior to protocol therapy), major treatment violations, or other reasons, and treat a total of 82 patients in order to ensure 72 evaluable patients at 24 months.

This study is designed as a non-inferiority/superiority “hybrid” design using the approach of Freidlin et al.[36] It is estimated that approximately 2/3 of the patients will undergo reconstruction. For patients who undergo mastectomy with immediate reconstruction, the rate of unplanned surgical complications at the Mayo Clinic is ~15% (personal communications with [name] and [name] 6/2014), comparable to what has been reported in the literature in the modern era.[27]. The rate of grade 3 or greater late toxicity in this population is expected to be $\leq 1\%$ (Whelan ASCO 2011). For the purpose of designing this trial, we will assume a 10% complication rate in the control arm. We consider that a 10% increase of this rate in the experimental arm would be acceptable (i.e. a non-inferiority margin of 10%). Based on the results of the START-B clinical trial[9], it is also plausible that toxicities in the experimental arm may even be reduced with the shortened fractionation schedule. Therefore, a marginal *decrease* in complication rate in the experimental arm to 5% (i.e. marginal benefit margin of 5%) may be reasonably expected. Denote p_0 and p_1 as the 24-month complication rate in the control arm and experimental arm, respectively. The null hypothesis is that the complication rate in the experimental arm is inferior to the control rate of 10% by more than 10% (i.e. $H_0: p_1 - p_0 > 10\%$). The alternative hypothesis is that the complication rate in the experimental arm is non-inferior to the control rate of 10% (i.e. $H_A: p_1 - p_0 < 10\%$).

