The primary analysis will occur after a minimum of 2-years following the enrollment of the last evaluable patient. The 24-month complication rate for each treatment arm will be estimated using exact binomial method along with a 1-sided 95% confidence limit. The approach of Freidlin et al. allows sequentially testing the hypotheses of non-inferiority and superiority in the same trial. Specifically, we will first test the non-inferiority hypothesis based on non-inferiority (NI) margin of 10%. If the upper bound of the 1-sided 95% confidence limit for $(p_1 - p_0)$ is larger than 10%,

then inferiority (of the experimental arm) cannot be ruled out. Otherwise, if the null hypothesis is rejected in favor of non-inferiority, then a test of superiority will be performed. Specifically, if the upper bound of the 1-sided 95% confidence limit for $(p_1 - p_0)$ is smaller than 0%, then superiority of the experimental arm is concluded; otherwise, if the upper bound of the 1-sided 95% confidence limit for $(p_1 - p_0)$ exceeds 0% but does not exceed 10%, non-inferiority without superiority will be concluded. No multiple-comparison adjustment is required for the two hypotheses tests.[36]

The operating characteristics of the proposed design are evaluated by carrying out 5,000 simulations. Using a one-sided type I error rate of 0.05 (corresponding equivalently to constructing a 1-sided 95% confidence limit), a study of 72 evaluable patients will have 80% power to reject the null hypothesis that the 24-month complication rate in the experimental arm is higher than that of the control arm by more than 10% (i.e. rule out inferiority) under the alternative hypothesis that the complication rate in the experimental arm is 5% less than that of the control arm (i.e. superiority). However, the design will have only 41% power when the two treatment arms are equivalent (i.e. the complication rate is 10% for both arms).

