16.6 Analysis Plan

The primary analysis will occur after a minimum of 2-years following the enrollment of the last evaluable patient.

16.61 Primary Analysis: The primary analysis will be to estimate the difference in the complication rate (grade 3+ toxicities, and unplanned surgical interventions) between the experimental arm and the control arm, which is defined as 24-month complication rate in experimental arm minus that in the control arm. All patients meeting the eligibility criteria who have signed a consent form and started treatment will be in the primary analysis. The complication rate will be estimated using a binomial estimator in both experimental arm and control arm, and a one-sided 90% confidence interval of the difference will be computed with normal approximation.

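### Does the normal-approximation limit for p1 − p0 in 16.61 exceed the stated 0.05 error by enough to require a score limit?

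*Combined protocol and SAP*

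**What the plan says.** Section 16.61 is the only place that names a method for the difference between arms: "a one-sided 90% confidence interval of the difference will be computed with normal approximation". The exact method in 16.4 is for each arm's own rate: "The 24-month complication rate for each treatment arm will be estimated using exact binomial method along with a 1-sided 95% confidence limit".

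The decision rule in 16.4 uses a one-sided 95% limit for the difference. "If the upper bound of the 1-sided 95% confidence limit for $(p_1 - p_0)$ is larger than 10"%, inferiority is not ruled out. The error rate is set in the same section: "Using a one-sided type I error rate of 0.05". The operating characteristics come from 5,000 simulations: "a study of 72 evaluable patients will have 80% power to reject the null hypothesis" when the experimental rate is 5 points below control, and "the design will have only 41% power when the two treatment arms are equivalent" (10% in both). No interval formula is given with those figures, and no attained error is reported.

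On numbers, 16.4 plans to "treat a total of 82 patients in order to ensure 72 evaluable patients at 24 months", while 16.61 analyses more broadly: "All patients meeting the eligibility criteria who have signed a consent form and started treatment will be in the primary analysis". The analysed set therefore lies between about 36 and 41 per arm.

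**The concern.** With 36 per arm and rates of 5% to 20%, each arm yields a handful of events. The usual unpooled (Wald) standard error is then often too small, the upper limit falls too low, and non-inferiority is declared too readily.

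The lean is in the unwelcome direction for a trial that asks whether a shorter schedule is safe enough. With 2 events of 36 in each arm, the Wald upper limit is 8.9% (non-inferior) and the score limit is 10.8% (not shown). If the excess were material, the plan would claim 0.05 without delivering it, and part of the stated power would be bought with extra error. A score limit is standard and needs only one sentence, so asking for it looks reasonable.

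**Working it through.** **Inputs.** From 16.4: control rate 10%, margin 10 points (so the null boundary is 20% v 10%), alternative 5% v 10%, equivalence 10% v 10%, 1:1 allocation, 72 evaluable (36 per arm), at most 82 treated (41 per arm), about two-thirds reconstructed. From 5.1: allocation balanced on immediate reconstruction. One-sided 95%, z = 1.645.

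**Rule.** Non-inferior if d + z·SE ≤ 0.10, where d is the observed rate difference and SE = √[p̂1(1−p̂1)/n + p̂0(1−p̂0)/n].

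**Step 1: the plan's power.** Closed form, power = Φ((0.10 − δ)/SE − 1.645):

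- 5% v 10%: SE = √[(0.0475 + 0.09)/36] = 0.0618; 0.15/0.0618 − 1.645 = 0.782; power 78.3%.
- 10% v 10%: SE = √(0.18/36) = 0.0707; 0.10/0.0707 − 1.645 = −0.231; power 40.9%.

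Enumerating all 37 × 37 outcomes gives 79.4% and 41.7%. Both agree with the stated 80% and 41%. The score limit gives 73.9% and 38.3%, and a 90% Wald limit 88.2% and 56.8%; neither matches. The stated power is therefore what a 95% Wald limit delivers.

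**Step 2: attained error, simple binomial sampling (exact).**

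| Per arm | True rates | Wald | Score |
|---|---|---|---|
| 36 | 20% v 10% | 5.5% | 5.0% |
| 41 | 20% v 10% | 6.3% | 5.0% |
| 36 | 15% v 5% | 6.5% | 4.7% |
| 41 | 15% v 5% | 7.4% | 4.8% |

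The last two rows assume a 5% control rate. In 16.4, 5% appears only as the hoped-for experimental rate. At the design boundary and planned size the excess is 0.0548 − 0.05 = 0.0048. The Monte Carlo standard error of 5,000 runs is √(0.0548 × 0.9452/5000) = 0.0032, so the excess is about 1.5 standard errors of the plan's own simulation.

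**Step 3: the trial's case mix.** Patients differ in risk and the arms are balanced on the main source of that difference, so the variance is below simple binomial. Assumed control rates are 14.5% with reconstruction and 1% without. At 24 + 12 per arm the overall rate is (24 × 0.145 + 12 × 0.01)/36 = 10.0%. The 10-point excess was placed wholly in reconstructed patients, by doubling both stratum rates, or as 10 points in each stratum.

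- 24 + 12 per arm: Wald error 4.7%, 4.7% and 5.2%. Power 79.6% and 41.3%.
- 27 + 14 per arm: Wald error 5.4%, 5.7% and 6.0%.
- Slightly uneven splits: 4.5-5.9% at 72 and 4.8-6.0% at 82.

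**Step 4: how often the method changes the verdict.** At 20% v 10%, Wald and score disagree in 0.5% of trials at 36 per arm and 1.3% at 41 per arm. Over arm splits within 2 of equal, the range is 0.3-2.3%.

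**Step 5: the price of a score limit (simple binomial).**

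| Per arm | Error removed | Power lost, 5% v 10% | Power lost, 10% v 10% |
|---|---|---|---|
| 36 | 5.48 − 5.01 = 0.5 points | 79.4 − 73.9 = 5.5 points | 41.7 − 38.3 = 3.4 points |
| 41 | 6.30 − 5.04 = 1.3 points | 85.5 − 79.4 = 6.1 points | 48.53 − 41.95 = 6.6 points |

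Stratifying the score limit by reconstruction leaves power at about 74% and 38% at 72 patients. The unstratified score limit first reaches 80% at 44 per arm (88 evaluable), more than the 82 to be treated.

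**The case for a change.** The best case for a change is this. At 36 per arm the Wald error exceeds 5% for every control rate from 6% to 22% (5.4-6.2%), while the score limit never exceeds 5.2%. Essentially every disagreement favours declaring the shorter schedule acceptable. Section 16.61 analyses all eligible treated patients, so the set may approach 82, and there the excess remains even with the case mix modelled (5.4-6.0%). The reassuring 4.7-5.2% rests on assumed stratum rates. The sentence has to be reopened for the 90%/95% conflict anyway, so naming a better limit adds little work.

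The direction of the lean and the 82-patient figures stand. They do not settle the choice. The excess stays near one point at the design rates, and 16.4 treats 82 precisely because it expects 72 with 24-month status. The score limit is not exact either: it reaches 5.2% unstratified, and its stratified form falls to 3.8%. It also takes power from a design that openly accepts 41% under equivalence. Keeping the named method and reporting its attained error is equally defensible. Sharing a sentence with the 90%/95% conflict is a matter of convenience and does not show that the method is wrong.

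**Conclusion.** No change is needed on this point. At one-sided 95%, the normal-approximation limit has an error of 5.5% (36 per arm) to 6.3% (41 per arm) under simple binomial sampling at 20% v 10%. With the balanced case mix and assumed stratum rates, the error is about 4.7-5.2% at 72 patients and 5.4-6.0% at 82. The stated 80% and 41% are right for this limit at 72. Moving to a score limit would exchange about 0.5 to 1.3 points of error for roughly 3 to 7 points of power, in a phase II trial deciding whether the schedule merits further study. Either choice is sound.

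This rests on three conditions. The limit must be taken at 95%: at the 90% printed in 16.61 the error is about 11.0% at 36 per arm, and that conflict with 16.4 has to be reconciled on its own account. The control rate must be near the assumed 10%; at 5% the Wald error is 6.5-7.4%. The stratum rates of 14.5% and 1% are assumptions chosen to give about 10% overall. Analysts can state the attained error beside the result without amending the plan.

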16.62 Secondary Analyses

16.621 *Acute adverse events (up to 90 days post-RT):* All patients who were registered to the study and started treatment will be included in the acute adverse event analysis. An acute adverse event is an AE, regardless of attribution, that occurs up to 90 days post-RT. The maximum grade for each type of acute AE will be recorded for each patient. Data will be summarized as frequencies and relative frequencies by treatment arm. Additionally, the relationship of the adverse event(s) to the study treatment will be taken into consideration.

16.622 *Late adverse events and reconstruction failure:* All patients who were registered to the study and started treatment will be included in the late adverse event and reconstruction failure analysis. A late adverse event is an AE, regardless of attribution, that occurs at least 90 days post-RT and up to 5 years post-RT. The maximum grade for each type of late AE will be recorded for each patient. Data will be summarized as frequencies and

relative frequencies by treatment arm. Additionally, the relationship of the adverse event(s) to the study treatment will be taken into consideration.

- 16.623 *Quality of life*: The subscales of the BCTOS, elements from CTCAE-PRO, and other patient reported measures such as fatigue, breast pain, breast shape, and arm related morbidity outlined in the appendix will be summarized as the mean \pm SD and median (minimum value, maximum value). Changes in the QOL measurements from baseline will be determined at each follow-up visit and measured by treatment arm. The comparison of the changes at each time point between the two treatment arms within each cohort will be done with a paired t-test or Wilcoxon signed rank test, whichever is appropriate.
- 16.624 *Cosmesis*: The values of the cosmesis instruments (patient self-reported and panel-assessed) will be summarized with the frequencies and confidence intervals of fair or poor cosmesis events at baseline, 2 years, and 5 years by treatment arm.
- 16.625 *IBTR incidence*: The IBTR cumulative incidence will be estimated using a competing risks method (Gooley et al.) by treatment arm. The competing risks will be regional/distant breast cancer recurrence and death.
- 16.626 *Regional recurrence incidence*: The regional breast cancer recurrence cumulative incidence will be estimated using a competing risks method (Gooley et al.) by treatment arm. The competing risks will be local/distant breast cancer recurrence and death.
- 16.627 *Distant recurrence incidence*: The distant breast cancer recurrence cumulative incidence will be estimated using a competing risks method (Gooley et al.) by treatment arm. The competing risks will be local/regional breast cancer recurrence and death.
- 16.628 *Disease-free survival*: DFS is defined as the time from registration until the time of disease recurrence or death due to any cause. The DFS will be estimated with a Kaplan-Meier estimator and curve by treatment arm. Estimates will be given for specific time points along with 95% CIs.
- 16.629 *Overall survival*: The OS will be estimated with a Kaplan-Meier estimator and curve by treatment arm. Estimates will be given for specific time points along with 95% CIs.
- 16.63 Exploratory Analyses: 2D and 3D strain parameters will be analyzed after radiotherapy compared to baseline and will be compared between patients undergoing conventional versus hypoofractionated radiotherapy. Continuous variable will be compared using unpaired t tests and nominal variables will be compared using contingency tables and Chi square analyses.
- 16.64 Correlative Analyses:

16.641 Cardiac toxicity

Cardiac toxicity remains an important late effect of radiotherapy for breast cancer.[3, 34, 37, 38] Echocardiography is a noninvasive tool that enables the detection of cardiovascular disease as a result of radiotherapy. Echocardiography can detect pericardial disease, left ventricular systolic and diastolic dysfunction, coronary artery disease suggested by resting or stress-induced regional wall motion abnormalities, and valvular heart disease.[33] Ideally, cardiac toxicity could be predicted prior to the onset of clinical symptoms to enable an earlier opportunity for risk stratification, surveillance, and preventative interventions that reduce risk. Echocardiographic strain rate imaging, a measure of regional myocardial function, has previously been reported to detect subclinical decline in cardiac function in the anterior wall of patients treated with radiotherapy for left-sided breast cancer.[34]

Patients requiring regional nodal irradiation, including treatment of the internal mammary lymph nodes, are at highest risk of developing radiation induced late cardiac complications such as coronary artery disease and myocardial infarction.[39] This is a result of a higher mean dose to the heart when dose the internal mammary lymph nodes are targeted.[3] Furthermore, many high risk patients are exposed to anthracyclines and HER2 directed therapies such as trastuzumab and pertuzumab which are also associated with cardiovascular toxicities [40]. Therefore, assessment of therapy-induced cardiac toxicity will be performed as outlined in section 4.0.

Cardiac imaging modalities have limitations such as cost and operator-dependency. In contrast, serum biomarkers are operator-independent and are a potentially lower cost, non-invasive means of predicting cardiac toxicity. In one prospective study of women undergoing adjuvant radiotherapy for breast cancer, mean cardiac troponin I (TnI) levels, a highly sensitive marker of cardiac damage, were significantly elevated after photon radiotherapy in left-sided patients compared to baseline, but not in right-sided patients.[34] However, other studies have not shown cardiac troponins to consistently be of clinical utility in this setting.[41, 42]. The natriuretic peptide N-terminal pro-B-type natriuretic peptide (NT-proBNP) has also been shown to be elevated in left-sided breast cancer patients after photon radiotherapy for breast cancer.[42] Similar to the case of cardiac troponins, results have been mixed and inconsistent.[41] There is no information available regarding the effects of scanning beam proton radiotherapy for breast cancer on these cardiac biomarkers. Blood will be drawn according to the schedule in section 4.0 to assess cardiac troponins and natriuretic peptides. Changes across time will be evaluated. In addition, blood will be stored for future testing of emerging biomarkers of radiation induced cardiac toxicity.

16.643 Molecular and Genomic Predictors of Fibrosis and Reconstruction Toxicity

Predictors of fibrosis and reconstruction failure are poorly understood. If a subset of patients at high risk of complications could be identified, their treatment could be personalized. Factors previously associated with worsened cosmesis after breast conserving therapy include inferior tumor location, large excision volume,

the presence of postoperative breast complications, higher dose (including radiotherapy boost), inhomogeneity, and use of concurrent chemotherapy.[43-45] We will analyze clinical and dose volume parameters correlated with increased risk of fibrosis and reconstruction failure following proton radiotherapy. However, clinical and dose-volume factors alone are not sufficient to explain the patient to patient variation in late toxicity following a course of radiation therapy.[46, 47] Indeed, patient specific molecular and genomic features may also be of significant importance in determining variation in normal tissue radiation response following breast cancer radiotherapy.

Cytokines and growth factors are involved in the radiation response and tissue remodelling and may serve as predictive factors for normal tissue damage. For example, levels of transforming growth factor β 1 (TGF- β 1) vary substantially between individuals and has previously been associated with radiation fibrosis in early-stage breast cancer patients.[48] TGF- β 1 is a multi-functional cytokine that attracts fibroblasts and stimulates collagen production.[49] Although basal levels may be important, expression levels of this protein are induced within an hour or less after exposure to ionizing radiation and therefore TGF- β 1 induction following radiation may be a better functional marker of an elevated fibrotic response.[50, 51] Therefore, blood will be drawn pre-treatment and on the last day of radiotherapy 1 hour following the final fraction. The pre and post radiotherapy levels of TGF- β 1 and other proteins in the fibrotic response will be compared and correlated with toxicity.

Mounting evidence also suggests that genetic variation may play an important role in determining susceptibility to radiation toxicity.[52] Radiogenomics is an emerging field aimed at studying genetic differences associated with variability in the effectiveness and toxicity of radiation.[47] We plan to use a candidate gene approach[47] to investigate the association of single nucleotide polymorphisms (SNPs), previously correlated with normal tissue toxicity, fibrosis, and reconstruction failure. For example, in addition to TGF- β 1, SNPs in the XRCC1 (codon 241) and XRCC1 (codon 399) genes, the protein products of which function in the DNA repair pathways of base excision repair and homologous recombination, respectively, have been correlated with increased risk of subcutaneous fibrosis following breast cancer radiotherapy. [REDACTED] laboratory at the Mayo Clinic has used a genome-wide association approach in human lymphoblastoid cell lines to identify radiation response biomarkers. C13orf34, MAD2L1, PLK4, TPD52, and DEPDC1B were identified and functionally validated as modifiers of radiation response. These promising findings, however, require further clinical validation, potentially as part of a meta-analysis of patients treated with breast cancer radiotherapy.[47, 53]

BRCA1 and *BRCA2* (*BRCA1/2*) germline mutations are responsible for the majority of hereditary breast cancer. The protein products encoded by *BRCA1/2* are essential members of the homologous recombination (HR) DNA repair pathway. *PALB2*, *ATM*, *CHEK2*, and *NBN* are other breast cancer predisposition genes that play important roles in HR. Emerging evidence suggests that HR-deficient cells are hypersensitive to protons.[54] Compared to x-rays, DNA repair is delayed following proton irradiation in HR-deficient, but not in wild-type cells.[55] Protons result in more clustered DNA DSBs, complex chromosomal aberrations, and an increased frequency of sister chromatid exchanges than x-

rays.[56, 57] These results suggest that the quality of DNA damage caused by protons has a greater requirement for DNA repair by HR. We will use emerging sequencing assays of known breast and ovarian cancer predisposition genes to develop preliminary data on whether patients with germline HR gene alterations are at increased risk of toxicity from proton therapy.[58] Flash frozen and paraffin embedded tumor and adjacent normal tissue will also be available through the breast spore to determine the impact of field effect cancerization toxicity outcomes.[59, 60] DNA will be extracted and HR gene sequencing analyses will be performed on tumor and adjacent normal tissue. Although event rates will likely be too low for definitive conclusions to be drawn, the impact of HR deficiency on disease control outcomes will also be assessed, potentially as part of a pooled analysis of breast, prostate, and pancreatic tumors treated with x-ray and particle therapy from multiple institutions. The final design of these future studies will depend on the event rates observed, cost and state of technology at the time.

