2.2 Secondary

2.2.1 To evaluate acute and late toxicity

2.2.2 To evaluate the rate of reconstruction failure (defined as loss of the tissue expander or implant with the inability to replace it resulting in no final reconstruction or conversion to autologous reconstruction or unplanned revision with the addition of autologous reconstruction).[27, 28]

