3.0 Patient Eligibility

3.1 Inclusion Criteria

- 3.12 Age \geq 18 years
- 3.13 Histologic confirmation of breast cancer resected by mastectomy with or without immediate reconstruction and chest wall and regional nodal irradiation planned.
- 3.14 pStage T1-T4N0-N3M0 or ypStage T0-4N0-N3M0
Note: The axilla must be staged by sentinel node biopsy alone, sentinel node biopsy followed by axillary node dissection, or axillary lymph node dissection alone
- 3.15 ECOG Performance Status (PS) 0 to 2. (Appendix I).
- 3.17 Radiotherapy must begin within 12 weeks of last surgery (breast or axilla) or last chemotherapy.
Note: Breast implants and expanders allowed
- 3.18 Able to and provides IRB approved study specific written informed consent
- 3.19a Ability to complete questionnaire (s) by themselves or with assistance
- 3.19b Able to complete all mandatory tests listed in section 4.0
- 3.19c Willing to return to enrolling institution for follow-up (during the active monitoring phase of the study)
- 3.19d Willing to provide tissue and blood samples for correlative research purposes.
- 3.19e Rochester and Arizona patients: Willing to sign consent onto the Mayo Clinic Radiotherapy Patient Outcomes Registry and Biobanking study, IRB number 15-000136
- 3.30 Rochester patients: Willing to sign consent onto Evaluation of cardiac function in patients undergoing proton beam or photon radiotherapy, IRB number 15-007443

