16.0 Statistical Considerations and Methodology

This is an open label phase II randomized controlled trial to determine the safety of 15 fraction vs 25 fraction scanning beam proton radiotherapy after mastectomy in patients requiring regional nodal irradiation.

16.1 Primary Endpoint:

16.1.2 Primary endpoint: 24 month complicate rate, defined as the percentage of women randomized who develop one or more of the following events:

- 1) grade 3 or higher late adverse events
- 2) unplanned surgical intervention (not including planned serial fat grafting) in patients who undergo mastectomy with reconstruction.

16.2 Secondary Study Endpoints: The secondary aims of this study are to characterize acute and late adverse events including grade ≥ 2 pneumonitis and reconstruction failure rate, assess patient self-reported cosmesis, evaluate fatigue, breast pain, arm function and other patient reported outcomes, compare the locoregional control, disease free, overall survival. Blood will be collected for future studies exploring dose volume and genomic predictors of adverse cosmesis and biomarkers of cardiotoxicity.

The following definitions are used for the secondary endpoints of interest:

- *Acute adverse events* (up to 90 days post-RT): any adverse event, regardless of attribution, that occurs in the first 90 days post-RT.
- *Late adverse events* (up to 5 years post XRT): any adverse event that occurred after the first 90 days post-RT and up to 5 years post-RT.
- *Reconstruction failure* (up to 5 years post XRT): loss of the tissue expander or implant with the inability to replace it resulting in no final reconstruction or conversion to autologous reconstruction or revised with the addition of autologous reconstruction.[27, 28]
- *Patient Reported Outcomes/Quality of life*: Elements of the Patient-Reported Outcomes Version of the Common Terminology Criteria for Adverse Events (PRO-CTCAE) will be used for patient self-reporting of toxicities. The Breast Cancer Treatment Outcomes Scale (BCTOS) will be used to measure patient reported functional status (pain, mobility). Other measures of fatigue, pain, and arm function are listed in the appendix.
- *Patient self-reported cosmetic outcomes*: the patient self-reported outcome will be assessed using a modified Harvard Cosmesis Scale and a modified BCTOS at baseline, 2 years, and 5 years.

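### Read literally, 16.622 counts patients with no expander or implant in the reconstruction failure rate, which would then be about two thirds of the rate in reconstructed patients

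*Combined protocol and SAP*

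**What the plan says.** Section 16.622 defines the analysis set for two endpoints in one sentence: "All patients who were registered to the study and started treatment will be included in the late adverse event and reconstruction failure analysis". The data are then to be summarised as frequencies and "relative frequencies by treatment arm". The section names no other set and does not state the denominator of the percentages.

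The objective in section 2.2.2 is "To evaluate the rate of reconstruction failure (defined as loss of the tissue expander or implant with the inability to replace it", followed by the consequences that make the loss a failure. Section 16.2 repeats the definition, "loss of the tissue expander or implant with the inability to replace it resulting in no final reconstruction" being its first part, and counts events up to 5 years after radiotherapy. Neither section gives a denominator.

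Section 3.13 admits patients whose tumour was "resected by mastectomy with or without immediate reconstruction". Section 16.4 states: "It is estimated that approximately 2/3 of the patients will undergo reconstruction". It also plans to "treat a total of 82 patients in order to ensure 72 evaluable patients at 24 months". Section 5.1 makes immediate reconstruction (yes or no) the only balancing factor in the minimisation.

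Elsewhere the plan does limit reconstruction outcomes to reconstructed patients. The surgical component of the primary endpoint in 16.1.2 is "unplanned surgical intervention (not including planned serial fat grafting) in patients who undergo mastectomy with reconstruction", and section 11.3.3 has nurses grade cosmesis only in women who are reconstructed.

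**The concern.** Every treated patient can have a late adverse event. Only a patient with an expander or implant can have a reconstruction failure as defined. Putting both endpoints on the all-treated set counts patients who were never at risk as successes.

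The primary composite does not have this difficulty to the same degree, because its other component, grade 3 or higher late adverse events, can occur in anyone. Reconstruction failure on its own has no such component.

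At stake is the reported value of a named secondary objective. Section 1.3 describes feasibility of hypofractionation with immediate implant-based reconstruction as a critical open question, and this rate bears directly on it. An all-treated denominator makes failure look rarer than it is in the patients concerned, and shrinks any absolute excess in either arm.

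**Working it through.** **Inputs from the plan**
- Treated patients: 82 (16.4), 1:1 allocation, so 41 per arm.
- Expected reconstructed share: s = 2/3 (16.4).
- Unplanned surgical complications in patients with immediate reconstruction: about 15% (16.4). This is not a failure rate.
- Assumed control complication rate, all patients: 10% (16.4).

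**Assumptions.** The documents give no reconstruction failure rate. I use 15% and 9% for illustration only.

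**1. The plan's own figure.** 2/3 × 15% = 10.0%, which matches the assumed 10% control rate. The plan does not say that it was obtained this way, but the same dilution is visible in its own numbers. Adding up to 1% for grade 3 or higher late toxicity gives 11.0%.

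**2. Patients not at risk.** 82 × 1/3 = 27.3 of the 82 treated. At risk per arm: 41 × 2/3 = 27.3.

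**3. Effect on the rate.** All-treated rate = s × rate in reconstructed patients.

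| Share s | 15% is reported as |
|---|---|
| 0.60 | 9.0% |
| 2/3 | 10.0% |
| 0.70 | 10.5% |
| 0.75 | 11.25% |

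At s = 2/3, 9% is reported as 6.0%.

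**4. Effect on the arm comparison.** With a patients reconstructed in the arm at 15% and b in the arm at 9%, and 41 treated per arm, the all-treated difference is (15a − 9b)/41 points. The true difference is 6 points and the true ratio is 15/9 = 1.67. The all-treated ratio is 1.67 × a/b.

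| a / b | Reported rates | Difference | Factor on difference | Ratio |
|---|---|---|---|---|
| 27 / 27 | 9.88% and 5.93% | 3.95 | 0.66 | 1.67 |
| 28 / 26 | 10.24% and 5.71% | 4.54 | 0.76 | 1.79 |
| 26 / 28 | 9.51% and 6.15% | 3.37 | 0.56 | 1.55 |

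The ratio is unchanged when the shares are equal, and moves by about 7% to 8% with a two-patient imbalance (28/26 = 1.077; 26/28 = 0.929). With equal true risks of 15%, a 28/26 split shows 10.24% and 9.51%. That gap of 0.73 points comes from the denominator alone and equals 0.3 of a patient in an arm of 41.

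**5. Price in precision.** On the 72 evaluable patients (36 per arm, 24 of them reconstructed), four failures in an arm are 4/36 = 11.1% (exact 95% CI 3.1% to 26.1%) or 4/24 = 16.7% (4.7% to 37.4%).

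**The case against.** The strongest reply is that 16.622 names an analysis set and stops there. It never states the denominator of the reconstruction failure percentage, and its wording closely follows that of 16.621, so the sentence may serve mainly to exclude patients who never started treatment. This stands in part: a reader might infer that a diluted rate is certain to be reported, and the text does not go that far. But all treated patients is the only set named, no other section narrows it, and the literal reading gives the diluted rate.

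Second, risk per treated patient is a legitimate summary, and the primary endpoint in 16.1.2 is itself a percentage of all women randomised. This also stands in part, and it is a reason to keep the all-treated rate as a supplement. It does not make that rate the answer to an objective about losing an expander or implant.

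Third, a reader might infer that the arm comparison is distorted. The documents do not support that as a general claim. Minimisation on immediate reconstruction should keep the shares close, so the ratio barely moves; the level of each rate and the absolute difference do shrink. Section 16.622 also reports counts, so the restricted rate could be recovered, but only if the number at risk per arm is shown, which it does not require.

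Fourth, simply restricting to reconstructed patients is not quite right either. Section 7.71 allows autologous reconstruction, and patients with that alone have no device to lose. Conversely, a patient with no device at radiotherapy may receive one later and lose it within the 5-year window. Both objections stand and shape the fix.

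**Conclusion.** The point holds for the literal reading of 16.622. At the planned 2/3 share, the reported failure rate in each arm and the absolute arm difference would be about 0.67 of their values in reconstructed patients. The factor that applies in practice is the observed share at risk: autologous-only reconstruction lowers it, and delayed expander or implant reconstruction raises it.

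The conclusion rests on three assumptions: that the relative frequencies use the stated analysis set as denominator; that the planning share is roughly met; and that every consequence listed in the definition follows from loss of an expander or implant. The 15% and 9% illustrate the arithmetic and are not estimates from the documents.

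A reader might go further and infer a threat to the trial's main result. There is none: the endpoint is secondary and descriptive, no test or decision rule uses it, and the primary analysis, sample size and margin are untouched. The amendment is still worth making, because for a descriptive endpoint the reported rate is the result. In an open-label trial, the denominator is better fixed before the data are seen.

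**What to change.** In 16.622, keep all treated patients for late adverse events and add a separate rule for reconstruction failure:

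- Report it by arm among treated patients with a tissue expander or implant in place at the start of radiotherapy, showing numerator and denominator.
- Leave patients with autologous-only reconstruction out of this denominator.
- List separately any failure after delayed expander or implant reconstruction, so that no event is lost.
- Optionally keep the all-treated rate as a supplementary figure, labelled as such.

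The cost is a few lines of text and a smaller denominator, at most about 27 rather than 41 per arm at the planned share, with wider intervals. Immediate reconstruction is already recorded for the minimisation (5.1), and section 18.1 lists a Breast Reconstruction form among the initial materials. Only the form's title is visible, so confirm that it records reconstruction type and status at the start of radiotherapy; if not, one item must be added.
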